## Background and Significance

Post-operative atrial fibrillation (POAF) is a common and potentially serious complication following cardiac surgery. Between 20-50% of patients experience atrial fibrillation (AF) often during the first week after surgery. POAF is not a benign condition. It is associated with a two- to four-fold increased risk of readmissions, renal failure, stroke, pacemaker implants, and bleeding. In addition, POAF carries a two-fold increase in all-cause 30-day mortality. POAF has long term implications. Of cardiac surgery patients who experience new onset AF, 18% had late AF at 1 year follow up, while 36% had AF at 5 years, and 55% had AF at 10 years. Accordingly, POAF may be an indication of an underlying myocardial substrate and represent a risk factor for developing sustained AF, rather than an unrelated post-surgical complication. POAF is not limited in its impact during the perioperative period, but rather, is associated with 4-fold risk of stroke and a 3-fold increase in all-cause mortality at 1 year. Patients who develop POAF incur on average \$10,000-\$20,000 in additional hospital treatment costs, 12-24 hours of prolonged ICU time, and an additional 2 to 5 days in the hospital. Indeed, the socioeconomic impact is profound. Healthcare costs related to the care of patients with POAF in the US are estimated at over \$1 billion annually.

Several prospective epidemiological studies have linked local and systemic inflammation with an increased risk of AF. The serological markers that have been most frequently studied are high-sensitivity C-reactive protein (CRP) and interleukin (IL)-6. Additional support for this concept has been suggested by multiple studies demonstrating decreased rates of POAF in patients who receive anti-inflammatory prophylaxis using corticosteroids. A growing body of literature details the unique features of the local intrapericardial postoperative inflammatory milieu after cardiac surgery as a possible contributor to POAF. Post-cardiotomy pericardial fluid has large (4 to 700-fold) increase of multiple circulating inflammatory factors, including tumor necrosis factor- $\alpha$ , neutrophil-gelatinase-associated lipocalin, myeloperoxidase, oncostatin M, and Metalloproteinases (MMP-9). Postoperative pericardial fluid is highly oxidative and contains blood, hemolyzed blood cells, free hemoglobin, and high levels of inflammatory markers reflective of leukocyte and platelet activation. Contact between inflammatory cells and cardiac tissue likely plays a role in the pathogenesis of POAF but the mechanisms of this interaction remain unknown. Animal models have illustrated that the incidence of POAF is directly correlated to the degree of inflammation of the atria and around the heart. Use of active clearance chest tubes has been shown to decrease incidence of POAF. Closing the pericardium following cardiac surgery also reduces the incidence of POAF.

There are several reports of human amniotic membrane (AM) reducing inflammation, having antimicrobial properties, and low risk of immunogenicity. This makes it an ideal biocompatible scaffold widely used for the treatment of several conditions, including intractable epithelial defects, burns, diabetic/ peripheral vascular ulcers, partial limbal cell deficiencies, peripheral nerve regeneration, tendon repair and Stevens-Johnson syndrome. AM is being used at our institution as a clinical tissue allograft in burn patients, for digital ulcers in scleroderma patients, as a nerve wrap to protect nerves from adhesions post-surgery, trachea stenosis-tracheal stent covering.

## Specific Aims

Cardiopulmonary bypass triggers a systemic and localized inflammatory response which has been shown to serve as a trigger for POAF onset. Some evidence further suggests that releasing the heart from its natural pericardial restraint can augment this response.

The Cell Therapy and Regenerative Medicine Program (CellReGen) at the University of Utah manufactures sterile AM for human use which is currently used to enhance wound healing, particularly in burn patients. Early investigation by our basic science laboratory has demonstrated that placement of AM on rat hearts after myocardial infarction can decrease myocardial scarring.

The primary objective of this research endeavor is to determine the safety of AM as a pericardial substitute in cardiac surgery with a secondary aim as to whether application of AM decrease the incidence of POAF following cardiac surgery. We hypothesize that application of AM at the time of cardiac surgery will decrease inflammation and the subsequent substrate for the development of POAF. In order to test this hypothesis, we

propose a pilot clinical trial in patients undergoing cardiac surgery at the University of Utah with the following specific aims:

**Aim 1. Safety of using AM in Cardiac Surgery:**

The AM applied epicardially will be assessed for ease of handling and applicability, signs of hyperacute rejection (e.g., membrane changing color), and clinical indications of a problem, such as cardiac tamponade or constriction assessed throughout the hospitalization and at post-operative follow-up.

**Aim 2: Compare incidence of POAF for until post-operative follow-up**

The incidence and burden of POAF will be assessed using 24 hour telemetry during hospital stay as well as a daily EKG reading at home between discharge and post-operative follow-up appointment.

**Aim 3: Comparison of inflammatory response: systemic and pericardial between patients who received AM and controls**

The proinflammatory response to cardiopulmonary bypass circuit as measured by numerous systemic and pericardial inflammatory markers i.e. C-reactive protein (CRP), TNF- $\alpha$ , Interleukin (IL)-6 and brain natriuretic peptide (BNP), have been linked to induction of atrial fibrillation in a number of previous publications. Hence, these markers were chosen for our study purposes. We will collect pericardial (from chest tubes) and systemic fluid markers at pre-specified intervals. We will assess the percentage change in the levels of the biomarkers as compared to their pre-operative baseline as there will be expected variability in the level of these biomarkers at baseline.

We have assembled a strong team that combines the expertise and resources of CellReGen, the clinical knowledge of the Divisions of Cardiothoracic Surgery and Cardiovascular Medicine, and the translational depth of the Cardiovascular Research and Training Institute (CVRTI). We expect that this focused clinical trial will provide the necessary data to expand the use of AM in a large scale, extra-murally funded multi-institutional trial.

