## Follow-up Evaluation

### a. Collection of inflammatory markers

The systemic and pericardial inflammatory markers, e.g., C-reactive protein (CRP), TNF- $\alpha$ , Interleukin (IL)-6 and brain natriuretic peptide (BNP), will be collected at the time of pericardiectomy. Pericardial fluid during surgery will be suctioned into a Luken trap directly from the pericardial sac. Postoperatively, the pericardial markers will be collected from the mediastinal chest tube drainage. The inflammatory markers will be collected at 24 hours, 48 hours, and 72 hours post-closing. These markers will be analyzed through ARUP.

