## Statistical Methods

We developed the statistical approach and determined sample size with the collaboration of [name], a biostatistician in the University of Utah Study Design and Biostatistics Center. We have a long history of collaborations with [name].

(Aim 1). The incidence of adverse events (AEs) will be reported as percentages, with two-sided 95% confidence intervals. Statistical comparisons of AEs between the AM treatment and the control group will be made using a chi-square, or Fisher's exact test, as appropriate (based on the minimum expected cell frequencies). These statistical comparisons, however, are known to be underpowered, and so the p values will be basically just descriptive. The user experience, such as ease of handling and applicability, will be reported descriptively.

(Aims 2 and 3). Since randomization will be used, simple significance tests should be sufficient, as the need to control for confounding will be essentially eliminated. Statistical comparisons of binary outcomes will be compared using a chi-square or Fisher's exact test, as appropriate. Statistical comparisons of continuous outcomes will be made using a two-sample t-test. If trends are observed in the expected direction (AM appears to be efficacious), this will support a conclusion of feasibility that justifies advancing to the next, larger study. Descriptive statistics will be reported to aid in sample size determination of the next, larger study.

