## Sample Size Justification

For a pilot study, where small sample sizes are used, a sample size of  $n = 12$  per group is recommended, because the standard error of the mean is known to decrease rapidly for each additional subject up to  $n = 12$ , after which diminishing returns sets in, with each additional subject having a noticeably smaller contribution to the reduction in the standard error. This means that statistical power is greatly improved by increasing the sample size up to  $n=12$ , but it takes substantial increases in the sample size beyond that to impact power appreciably. For the efficacy aims (Aims 2 and 3), then,  $n=12$  per group is sufficient to detect trends from statistical comparisons without unduly increasing the size of the study. We will use  $n=20$  per group, however. This provides 80% power to detect a 0.80 SD difference in means, using a two-sided alpha 0.10 comparison. If the effect is large, then, we will likely see at least marginally statistical significant differences. Statistical significance is not needed, however, for a pilot feasibility study, as only a trend in the expected direction is required. Also, the  $n=20$  per group is large enough to provide reasonably stable estimates of means and standard deviations for sample size determination for the next, larger study. (Aim 1) The  $n=20$  per group provides a reasonable opportunity to detect adverse events (AE) in the AM treatment group. Intuitively, if the AE is common, 1/20 or 5%, it seems that at least 20 subjects should be used to detect 1 event (1 out of 20). The exact probability is determined by the binomial probability formula,

$$\begin{aligned} & \text{Prob(at least 1 event is observed | probability is 1/20)} \\ &= 1 - \binom{N}{n} p^n (1-p)^{N-n} = 1 - \binom{20}{0} p^0 (1-p)^{20-0} = 1 - (1)(1)(.95)^{20} = 1 - .358 \\ &= .64 \text{ or } 64\% \end{aligned}$$

So, if the probability of an AE is 1/20, or 5%, we will have a 64% probability of observing at least one AE in our AM treatment group. To increase the probability to 90% would require  $n = 45$  per group, which is unreasonable. That is, it is more ethical to use fewer subjects at this stage of the product development, in case the risk of an AE is even higher. Furthermore, if the risk of the AE is very high 1/10, or 10%, we have an 88% probability of observing an AE with our  $n=20$ .

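### Aim 3 tests percentage change from baseline with an unadjusted t-test; if the markers are roughly log-normal, log-scale ANCOVA on the baseline already collected would be more precise at little cost

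*Combined protocol and SAP*

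**What the plan says.** Specific Aims, Aim 3, defines the outcome: "We will assess the percentage change in the levels of the biomarkers as compared to their pre-operative baseline". The reason given is that patients are expected to differ at baseline. Statistical Methods (Aims 2 and 3) supplies the test: "Statistical comparisons of continuous outcomes will be made using a two-sample t-test". It defends unadjusted testing on the ground that, under randomisation, "simple significance tests should be sufficient, as the need to control for confounding will be essentially eliminated". No log transformation, baseline covariate or ANCOVA is mentioned anywhere.

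On size, Sample Size Justification says of 20 per group: "This provides 80% power to detect a 0.80 SD difference in means, using a two-sided alpha 0.10 comparison". It adds that significance is not needed in a pilot and that "only a trend in the expected direction is required". On the use of the results: "Descriptive statistics will be reported to aid in sample size determination of the next, larger study".

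On sampling, Follow-up Evaluation, item a, says that the first markers "will be collected at the time of pericardiectomy", and adds: "Pericardial fluid during surgery will be suctioned into a Luken trap directly from the pericardial sac". Later samples are at 24, 48 and 72 hours, with the pericardial ones taken from chest tube drainage. The membrane goes on at the end of the operation (Surgical application/implantation of AM).

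**The concern.** Varying baselines are a good reason to use the baseline, but dividing by it is an inefficient way to do so. The ratio carries all the noise of the baseline into the outcome, and it is right-skewed when both values are. Adjustment uses only as much of the baseline as predicts follow-up. The randomisation argument in Statistical Methods deals with bias; it does not address precision.

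The loss is largest when baseline and follow-up are weakly correlated. That is possible for the pericardial markers, because the first sample comes from the sac and the later ones from drainage. With 20 patients per arm, what is at stake is power to see a marker effect and, to a smaller degree, the stability of the spread estimates carried into the next study.

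The Aim 3 text also calls the baseline pre-operative, whereas the first sample in the collection schedule is intra-operative. The plan should say which sample is the baseline for each fluid.

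**Working it through.** **1. The plan's own figure.** For n = 20 per group, a difference of 0.80 SD and two-sided alpha 0.10, the noncentrality is 0.80 × √(20/2) = 2.530 on 38 df, with critical value 1.686. Power is 0.799, which reproduces the stated 80%. It is expressed in SDs of the outcome tested. It therefore does not say how large a marker effect 0.80 SD of percentage change represents.

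**2. Variance on the log scale.** Let s0 and s1 be the log-SDs at baseline and follow-up, and ρ their correlation.
- Log change: s0² + s1² − 2ρ·s0·s1
- ANCOVA residual: s1²(1 − ρ²)

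With equal SDs the ratio of ANCOVA to log change is (1 + ρ)/2, which is 0.65, 0.75 and 0.85 at ρ = 0.3, 0.5 and 0.7. With s0 = 1.0, s1 = 0.7 and ρ = 0.3 it is 0.446/1.070 = 0.42. With s0 = 0.4, s1 = 0.8 and ρ = 0.5 it is 0.48/0.48 = 1.00, so adjustment adds nothing beyond taking logs.

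**3. Simulation.** From the plan: 20 per arm, two-sided alpha 0.10, t-test on percentage change. Assumed, because the documents give no values: bivariate log-normal markers, the SDs and correlations below, and an effect of 0.80 SD of log follow-up. There were 20,000 trials per scenario. Power (%) is shown as percentage-change t-test / log-change t-test / log-ANCOVA. The last column is the n per arm that percentage change needs to match log-ANCOVA at 20 per arm (8,000 to 12,000 trials per step).

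| s0, s1 | ρ = 0.3 | ρ = 0.5 | n to match (ρ = 0.3; 0.5) |
|---|---|---|---|
| 0.3, 0.3 | 65.7 / 67.7 / 82.5 | 78.3 / 79.8 / 88.3 | 31; 27 |
| 0.4, 0.4 | 64.9 / 68.2 / 82.7 | 77.7 / 80.3 / 88.4 | 33; 29 |
| 0.6, 0.6 | 60.7 / 67.9 / 82.2 | 74.7 / 79.8 / 88.1 | 37; 30 |
| 1.0, 1.0 | 50.1 / 67.9 / 82.5 | 66.0 / 80.0 / 88.1 | 52; 41 |
| 1.0, 0.7 | 39.8 / 51.7 / 82.4 | 52.1 / 62.3 / 88.5 | 72; 59 |
| 0.4, 0.8 | 73.3 / 81.5 / 81.8 | 83.3 / 89.2 / 88.2 | 27; 24 |

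The matching range is therefore about 24 to 72 per arm. Its upper end (59 to 72) arises only where the baseline is noisier than follow-up (1.0 against 0.7).

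At ρ = 0.7 with equal SDs of 0.3 to 1.0, power is 88–94% against 96%; with SDs 1.0 and 0.7 it is about 71–72% against 96%. At ρ = 0.9 with equal SDs the two are the same.

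Type I error stayed near 0.10 on the grid without the 0.4/0.8 pair: 0.086–0.104 for percentage change and 0.097–0.106 for log-ANCOVA. Both tests are valid.

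**4. Where the gain comes from.** Where the baseline is at least as variable as follow-up and ρ is 0.3 to 0.5, logs alone add 2 to 18 points and adjustment a further 8 to 31. In the 0.4/0.8 case logs give nearly all of the gain.

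**5. Other criteria, ρ = 0.3 to 0.5.** The observed trend had the right sign in about 91–99% of trials with percentage change and over 99% with log-ANCOVA. For planning, I took the squared coefficient of variation of the post/baseline ratio in the control arm. Its 90th-to-10th percentile span was 2.7- to 4.5-fold, against 2.3- to 2.4-fold for the log-scale variances.

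**6. Cases that weaken the point.** If half of the baseline values sit at an assay floor, power is 74% against 81% (SDs 0.6, ρ = 0.3), 82% against 86% (SDs 0.6, ρ = 0.5) and 68% against 81% (SDs 1.0 and 0.7, ρ = 0.3). If the post/baseline ratio is normal (mean 10, SD 3, difference 2.4, independent of baseline), percentage change is better: 80–81% against 74–75%.

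**The case against.** The strongest reply is that this is a pilot with safety as its primary objective. Simple tests were chosen on purpose with a biostatistician, and the decision rule asks only for a favourable trend. Most of that stands: significance is not the criterion, and the sign of the trend is usually right under either analysis.

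It is also fair that every power gap rests on assumed inputs. The 4- to 700-fold rises cited in Background and Significance make a multiplicative scale plausible for pericardial factors, but do not establish log-normality. In addition, log-scale SDs can be computed later from the same raw data, and logs alone remove the instability in the planning estimates. What the reply leaves untouched is that the stated defence concerns confounding, and that a more precise analysis needs no new data.

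Three stronger readings are tempting, and the documents do not support them:
- **That the 80% is wrong, or the t-test invalid.** The figure reproduces, and type I error is close to nominal.
- **That the baseline is contaminated by treatment.** The first sample precedes placement of the membrane, so it is usable as a covariate. The loose label is missing detail and adds no weight to the ANCOVA argument.
- **That the go-ahead, or the sizing of the next study, would be misled.** The first is little affected, and the second is a modest and recoverable cost.

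**Conclusion.** This stands as a modest efficiency improvement and not as an error. On log-normal markers with correlation 0.3 to 0.5, percentage change gives about 40–83% power where log-scale ANCOVA gives 82–89%. The gap narrows as correlation rises and vanishes at 0.9 with equal SDs.

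The size depends on assumptions the documents cannot settle: distribution, SDs, correlation, and an effect defined on the log follow-up scale. The gain shrinks if many values are at an assay floor and reverses by 5 to 6 points if the ratios are normally distributed. Confidence is medium; this is for the sponsor to consider.

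**What to change.** In Statistical Methods, make the Aim 3 analysis an ANCOVA of log(marker) at 24, 48 and 72 hours, or one repeated-measures model. Use as covariate the log of the pre-implant sample of the same fluid. State, separately for blood and pericardial fluid, whether that baseline is a pre-operative value or the sample taken at pericardiectomy. Add a rule for values below the detection limit.

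Report the membrane-to-control geometric mean ratio with its confidence interval, and the log-scale residual SD and baseline correlation for planning the next study. Keep percentage change as a descriptive summary.

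The cost is some wording in the analysis plan and slightly more analysis work, with no new samples or patients. The downside is the possible 5- to 6-point loss of power if post/baseline ratios turn out to be normally distributed.

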### **Research Design and Methods**

All patients enrolled in the study will undergo the standard procedures as part of the surgical preparation and follow-up. The study is comprised of five main time periods: 1) Pre-operative screening 2) manufacturing and storage of hAM, 3) surgical application/implantation with hAM, 4) follow up and evaluation of postoperative efficacy of hAM, 5) collection and analysis of clinical data.

**Preoperative screening** We will enroll 40 patients undergoing elective coronary artery bypass grafting (CABG). The successfully screened cohort will be randomized to (20 patients in each arm): Interventional arm (patients who will have AM placed epicardially) and control arm (pericardial closure over great vessels and base of right ventricle, leaving the bottom part uncovered).

A pre-surgical echocardiogram will be conducted to evaluate ejection fraction, valvular dysfunction, cardiomyopathy, chamber dimensions, cardiac motion, and strain. Candidate predictor variables (patients' demographic features and clinical risk factors), echocardiographic parameters like atrial dimensions and ejection fraction, CHA2DS2-VASc score, and other patient factors will be collected.

**Inclusion Criteria:** Patients undergoing primary elective CABG at the University of Utah Hospital; Patients 18 years or older; Ability to provide informed consent and follow-up with protocol procedures

**Pre-operative Exclusion Criteria:** Patients in AF at the time of surgery; Prior history of sternotomy; Prior history of pericarditis; Currently on aggressive antiarrhythmic therapy (does not include beta blockers); Patients with an implantable cardiac device (pacemaker, ICD, CRT-D), ejection fraction <45%.

Patients will be randomly assigned 1:1 to the control group or the study treatment group through a computer system, REDCap, to eliminate biased treatment assignments.

**Manufacturing and storage of AM:** Amnion is processed from placenta that is procured from volunteer donors according to protocols approved by the Institutional Review Board at the University of Utah. The birth tissue is placed into a sterile plastic receptacle that contains 0.9% Sodium Chloride and is transported to CellReGen for processing. The amniotic membrane is carefully separated from the chorion using blunt finger dissection. Two 2x2 cm^2 sections are cut from the amnion for sterility testing. The amnion is sent for gamma irradiation. After return of the irradiated amnion, an inspection of the product is made and the packaged membrane is stored in quarantine until the donor's medical and donor screening answers and their infectious disease testing results are reviewed and signed-off by the Medical Director, QA Specialist and Scientific Director. The customized 7x15 cm sized, rectangular shaped GMP-grade wet AM placed on Telfa gauze will be provided inside the foil pouch for this clinical trial.

**Surgical application/implantation of AM:** The packaged wet AM placed on Telfa gauze inside of a foil pouch, will be transferred from CellReGen to the OR. At the end of planned cardiac surgery, the size and shape of customized 7x15 cm AM can be easily adjusted according to the size of the pericardium defect.

## Follow-up Evaluation

### a. Collection of inflammatory markers

The systemic and pericardial inflammatory markers, e.g., C-reactive protein (CRP), TNF- $\alpha$ , Interleukin (IL)-6 and brain natriuretic peptide (BNP), will be collected at the time of pericardiectomy. Pericardial fluid during surgery will be suctioned into a Luken trap directly from the pericardial sac. Postoperatively, the pericardial markers will be collected from the mediastinal chest tube drainage. The inflammatory markers will be collected at 24 hours, 48 hours, and 72 hours post-closing. These markers will be analyzed through ARUP.

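### Later pericardial markers exist only while the chest tube drains, so t-tests at 48 and 72 hours compare patients selected after randomisation, with possible bias in either direction

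*Combined protocol and SAP*

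**What the plan says.** Aim 3 states: "We will collect pericardial (from chest tubes) and systemic fluid markers at pre-specified intervals". The section on collection of inflammatory markers confirms the source ("Postoperatively, the pericardial markers will be collected from the mediastinal chest tube drainage") and sets the times: "The inflammatory markers will be collected at 24 hours, 48 hours, and 72 hours post-closing". The intraoperative pericardial sample is taken from the sac itself, so it does not need a tube. The endpoint is relative to baseline: "We will assess the percentage change in the levels of the biomarkers as compared to their pre-operative baseline".

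Post-operative care follows usual practice: "All patients enrolled in the study will undergo the standard procedures as part of the surgical preparation and follow-up". The documents give no tube duration, no rule for a tube that is out or dry at a sampling time, no second pericardial source, no missing-data method and no preferred time point.

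For the analysis, Statistical Methods says "Statistical comparisons of continuous outcomes will be made using a two-sample t-test", on the ground that "Since randomization will be used, simple significance tests should be sufficient, as the need to control for confounding will be essentially eliminated". The same section treats a favourable trend as enough to justify the larger trial. Sample Size Justification bases its power statement on all 20 patients per arm.

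**The concern.** Randomisation protects a comparison of everyone randomised. It does not protect a comparison of the subset whose tube is still yielding fluid two or three days after closure, because membership of that subset is settled after allocation. The plan's reason for using simple tests therefore does not cover the late pericardial samples.

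An effect of the membrane on that state is plausible from the documents, though not shown. Specific Aims hypothesises that AM reduces inflammation, and Strengths and Limitations lists tamponade and constriction as possible complications.

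Two things are at stake. Selection that differs by arm would shift the trend itself, and the pilot is to be read on its trends. The same means and SDs are also meant to size the next trial, so a distortion would carry forward.

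**Working it through.** **Plan's own figure.** Inputs from Sample Size Justification: n = 20 per arm, difference d = 0.80 SD, two-sided alpha 0.10, power 80%. The noncentrality is d/√(2/n) = 0.80/√(2/20) = 2.530 and the critical t on 38 df is 1.686. Noncentral-t power is 79.9%, so the 80% reproduces if all 20 patients per arm give a sample.

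**A. Precision only: equal loss, same selection in both arms.** The removed share is an assumption. The same formula gives:

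| Removed | n per arm | Noncentrality | Critical t | Power |
|---|---|---|---|---|
| 25% | 15 | 2.191 | 1.701 | 69% |
| 50% | 10 | 1.789 | 1.734 | 53% |
| 75% | 5 | 1.265 | 1.860 | 32% |

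Here bias is zero.

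**B. Bias only: unequal retention, true difference 0.80 SD.** Assumptions: drainage and marker are bivariate normal with correlation ρ = 0.3 to 0.5; AM lowers mean drainage by s = 0.4 to 0.8 SD; a sample exists only above a common drainage threshold, set so that the stated share is out over both arms together. With a the threshold in an arm's own SD units and p the share retained, λ = φ(a)/p, and

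observed difference = 0.80 − ρ(λ_AM − λ_control).

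| Out overall | s | Retained, control v AM | λ control, AM | ρ | Observed (original SD) |
|---|---|---|---|---|---|
| 25% | 0.4 | 81% v 69% | 0.331, 0.515 | 0.3 | 0.74 |
| 25% | 0.8 | 87% v 63% | 0.242, 0.600 | 0.5 | 0.62 |
| 50% | 0.4 | 58% v 42% | 0.675, 0.929 | 0.3 | 0.72 |
| 50% | 0.8 | 66% v 34% | 0.562, 1.069 | 0.5 | 0.55 |
| 75% | 0.4 | 31% v 19% | 1.132, 1.436 | 0.3 | 0.71 |
| 75% | 0.8 | 37% v 13% | 1.019, 1.630 | 0.5 | 0.49 |

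For example, 0.80 − 0.5 × (1.069 − 0.562) = 0.55. Simulation with one million patients per arm agrees to within 0.01.

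Truncation also shrinks the SD: the variance in an arm becomes 1 − ρ²λ(λ − a). In the 50%, s = 0.8, ρ = 0.5 case (a = −0.40 and 0.40) the variances are 0.865 and 0.821, the root of their mean is 0.918, and 0.547/0.918 = 0.60. In the SD of the sampled patients the three ranges are 0.66 to 0.76, 0.60 to 0.75 and 0.55 to 0.73.

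**C. Direction: no true effect, ρ = 0.5.** Retaining 60% of controls and 40% of AM gives λ = 0.644 and 0.966, so the bias is 0.5 × (0.966 − 0.644) = 0.16 SD against AM. In 40,000 simulated trials (12 v 8 patients) AM looked lower in 35% instead of 50%. With retention reversed it looked lower in 65%. The nominal 10% test rejected in about 12%.

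A and B are separate scenarios. The 5-per-arm power does not belong with the 0.49, which comes from about 7 controls and 3 AM patients.

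**The case against.** The documents do not say when tubes come out. If nearly all drained to 72 hours, the selection and the power loss would largely vanish. A reader might infer that the 72-hour test will have far fewer than 20 per arm; nothing in the text supports that as fact.

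A reader might also infer that the late comparison is biased toward no effect because the AM patients still draining are its worst cases. That needs AM to lower drainage and drainage to rise with marker level. Neither is stated: the hypothesis concerns inflammation, not drainage volume, and the named complications mean drainage could move either way.

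Power also carries limited weight here. The 80% is a general statement about a difference in means, the plan says significance is not required, and it regards 12 per group as enough to see trends. With a true 0.80 SD, 10 per arm and no bias, the observed difference has the right sign with probability Φ(1.789) = 96%. In the 50%-out scenarios of B it is still about 90% to 95%, falling to about 78% to 87% only at 75% out.

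Finally, the scope is narrow. Safety is the primary objective, and neither the blood markers nor the intraoperative pericardial sample needs a tube.

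All of this stands and limits the size of the point. It does not remove it: no passage says what happens when a tube is out, and when the true effect is small or absent, as in C, selection can change which way the trend points.

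**Conclusion.** The point holds conditionally. The late pericardial samples depend on a post-randomisation state, and the plan's appeal to randomisation does not cover t-tests restricted to patients in that state. Bias requires both that retention (or the way patients are selected) differs by arm and that drainage is related to marker level. Its direction cannot be known in advance, and if AM raised drainage the attenuation in B would reverse. With the same selection in both arms, the harm is lost precision and a narrower population.

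The ranges above show what could happen under assumed removal shares, correlations and drainage shifts; they are not estimates for this trial. The 24-hour sample shares the dependence, but loss from tube removal cannot be greater then than later. Severity is modest because this is the third aim of a pilot.

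**What to change.** Changes to the marker-collection section and Statistical Methods, made before any marker data are seen:

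- Name the 24-hour sample as the main pericardial comparison.
- Analyse 24, 48 and 72 hours in one mixed model for repeated measures using all available samples, in place of a t-test at each time.
- Record drainage volume and tube-removal time, and report the samples available by arm at each time.
- Label the 48- and 72-hour pericardial results supportive and conditional on a draining tube. Add a sensitivity analysis for missing samples: the mixed model assumes missing at random, so it reduces the bias rather than removing it.
- Use the blood markers for the full randomised comparison at 72 hours, worded as a systemic and not a pericardial conclusion.

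No change to tube management is proposed. The cost is a little more data entry and analysis, with no added patients or visits. The downside is that the late pericardial comparison becomes supportive only, although the rationale in Background and Significance is partly about the local pericardial environment.
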